### **5.8.1. Adverse Events**

In general, the primary focus of AE reporting will be on TEAEs summarized in TEAE period. Post-treatment AEs will be summarized separately.

If an AE onset date (occurrence, worsening, or becoming serious) is incomplete, an imputation algorithm will be used to classify the AE as pre-treatment, treatment-emergent, or post-treatment. The algorithm for imputing date of onset will be conservative and will classify an AE as treatment-emergent unless there is definitive information to determine pre-treatment or post-treatment status. Details on classification of AEs with missing or partial onset dates are provided in Section 6.3.

Adverse event incidence tables will present the number (n) and percentage (%) of patients experiencing an AE by SOC and PT. In addition, incidence tables by SOC, HLGT, HLT, and PT will be provided for all TEAEs, serious TEAEs, and TEAEs leading to permanent treatment discontinuation. Multiple occurrences of the same event in the same patient will be counted only once in the tables within a treatment phase (TEAE or post-treatment AE). For tables presenting by severity of events, the worst severity will be chosen for patients with multiple instances of the same event. The denominator for computation of percentages is the safety analysis set within each treatment group.

AE incidence tables will present data by SOC sorted alphabetically and PT sorted by decreasing frequency of the overall patient, and summarize the number (n) and percentage (%) of patients experiencing an AE.

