8.3.2. Study Drug Discontinuation

Patients who permanently discontinue from study drug should be encouraged to remain in the study. Those who agree and do not withdraw from the study will be asked to return to the clinic for all remaining study visits and assessments per the visit schedule, especially the week 52 visit, including the off-drug follow-up visits ([Table 1](#) and [Table 2](#)).

Patients who permanently discontinue from study drug and who opt to withdraw from the study (ie, are unable or unwilling to attend the study visits as described above) will be asked to complete study assessments at an early termination (ET) visit, per Section [9.1.2](#). These patients will then enter the off-drug treatment follow-up period, and should be followed for at least 20 weeks from the last dose of study drug or up to recovery or stabilization of any AE to be followed-up as specified in this protocol, whichever comes last. The off-drug follow-up period will include 2 in-clinic visits with assessments as specified under visit 16 and visit 17 ([Table 2](#)).

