### **2.3. Study Plan**

The study consists of 3 periods: a screening period, a DBTP, and a safety follow-up period. The screening period of up to 28 days will determine participant eligibility and will include an evaluation of prior episodes of HTG-associated AP, genotyping to exclude patients with FCS due to LoF mutations in LPL, and a measurement of fasting TG level. Patients must have baseline fasting TGs  $>880$  mg/dL and a history of HTG-associated AP within 24 months of screening or they must have baseline fasting TGs  $>500$  mg/dL if they have had 2 or more episodes of HTG-associated AP within 24 months of screening or if they have had baseline fasting TG values  $>500$  mg/dL and documented fasting TG values  $>1000$  mg/dL with a history of HTG-associated AP within 24 months of screening to be enrolled in the study.

[figure not shown]
Patients who fulfill all the eligibility criteria will be randomized and receive their first dose of assigned study drug on day 1, with subsequent doses administered approximately Q4W during the 52-week DBTP. This will be followed by an off-drug follow-up period of 20 weeks. Every effort will be made to keep patients in the study and to collect the week 52 visit data, even if study drug administration has been discontinued for the patient.

Approximately 120 adult patients will be randomized 1:1 to receive evinacumab or matching placebo. A study schematic is provided in [Figure 1](#).

Efficacy will be assessed by measuring the number of patients with at least 1 independently adjudicated positive event of AP over 52 weeks of treatment with evinacumab versus placebo. The study will have an independent committee to adjudicate these episodes in accordance with clinical standards for diagnosis of AP (see Section 4.7.1). Efficacy will also be assessed by clinical laboratory evaluation of lipid levels at pre-specified time points throughout the study.

Safety will be assessed throughout the study by comparing the frequency and severity of adverse events (AEs) between the evinacumab and placebo groups, as well as evaluating abnormal laboratory findings, ECG findings, and ADA and NAb assessments.

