#### **4.8.1. Adverse Events Variables**

The period of safety observation starts from the time when the patient gives informed consent and continues into the following periods:

- The pre-treatment period is defined from the day the ICF is signed to the day before the first dose of study treatment administration.
- The treatment-emergent adverse event (TEAE) period is defined from the day of the first study treatment administration to the day of the last study treatment administration + 168 days (24 weeks).
- The post-treatment period is defined from the day after the end of the TEAE period to the last study visit.

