***Post-treatment adverse events***

- All post-treatment AEs by primary SOC and PT
- All post-treatment SAEs by primary SOC and PT

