***Patient Deaths***

The following summaries of deaths will be generated.

- Number (%) of patients who died by study period (TEAE and post-treatment) and reason for death;
- TEAEs leading to death (death as an outcome on the AE CRF page, as reported by the Investigator) by SOC and PT

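### Post-treatment adverse event percentages are taken over the whole safety set, although most patients can contribute little or no post-treatment time, so 0% cannot be told apart from not observed

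*SAP*

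**What the plan says.** SAP 4.8.1 runs the treatment-emergent period from first dose "to the day of the last study treatment administration + 168 days (24 weeks"). It then says: "The post-treatment period is defined from the day after the end of the TEAE period to the last study visit".

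SAP 5.8.1 sets one denominator for adverse event incidence tables: "The denominator for computation of percentages is the safety analysis set within each treatment group". The paragraph is not confined to treatment-emergent events. It says that repeat events in a patient "will be counted only once in the tables within a treatment phase (TEAE or post-treatment AE"). The tables planned under the post-treatment heading include "All post-treatment AEs by primary SOC and PT" and the same for SAEs.

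For deaths the SAP plans "Number (%) of patients who died by study period (TEAE and post-treatment) and reason for death". No denominator is named there. The general rule in SAP 5.8, that safety summaries use the safety analysis set, implies the same one.

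Membership of the safety set (SAP 3.2) needs only one full or partial dose. It does not depend on being followed into the post-treatment period. The SAP gives no count of patients at risk and no exposure-adjusted rate for the post-treatment tables.

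**The concern.** A percentage is readable when the patients in its denominator could have had the event counted in its numerator. Here the treatment-emergent window absorbs the off-drug follow-up almost exactly, so a patient who takes the full course has almost no time in which a post-treatment event could be recorded. That patient still counts in full in the denominator.

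Two misreadings follow. First, a cell showing 0 (0%) can mean that patients were watched and nothing happened, or that nobody was watched. Printing n beside the percentage does not resolve this. Second, the percentage equals the share of patients who enter the period times the risk among those who enter. If the arms differ in how many patients stop drug and remain in the study, the percentages differ even when the risk is the same.

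Two features of the SAP sharpen the point. Incomplete onset dates default to treatment-emergent (SAP 5.8.1 and 6.3), which tends to empty the post-treatment tables further. And for laboratory abnormalities SAP 5.8 already applies the appropriate principle: its denominator is limited to patients with at least one assessment of the parameter in the period. Post-treatment events get no equivalent.

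**Working it through.** **Inputs**
- Treatment-emergent window after last dose: 168 days (SAP 4.8.1).
- Dosing: "subsequent doses administered approximately Q4W during the 52-week DBTP" (SAP 2.3). The schedule table in SAP 10.4 has 13 doses on Days 1 to 337, with a window of ±4 days.
- Final visit: Week 72, Day 505 ±7 days (SAP Table 3, Protocol Table 2). SAP Table 1 also targets Day 505.
- Patients who stop drug and stay are asked to attend all remaining visits (Protocol 8.3.2).
- Patients who stop drug and withdraw "should be followed for at least 20 weeks from the last dose of study drug", or until a followed event has recovered or stabilised, whichever is later (Protocol 8.3.2).

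**The plan's own days reproduce.** 24 × 7 = 168. Last dose: 48 × 7 + 1 = Day 337. Final visit: 72 × 7 + 1 = Day 505.

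**Formula.** Post-treatment days = max(0, last visit day − (last dose day + 168)).

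**Full course, nominal days.** 337 + 168 = 505, and 505 − 505 = 0 days.

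**Full course, within windows.** The dose can be up to 4 days early and the final visit up to 7 days late, so the maximum is 4 + 7 = 11 days. Giving equal weight to all 9 × 15 = 135 combinations (an assumption), 63 give at least one day (46.7%). The positive days total 282, so the mean is 282/135 = 2.09 days.

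**Stop early and stay to Day 505**

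| Last dose (week) | Last dose day | Window ends (day) | Post-treatment days |
|---|---|---|---|
| 0 | 1 | 169 | 336 |
| 12 | 85 | 253 | 252 |
| 24 | 169 | 337 | 168 |
| 36 | 253 | 421 | 84 |
| 44 | 309 | 477 | 28 |
| 48 | 337 | 505 | 0 |

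Each missed final dose adds 28 days.

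**Stop and withdraw, minimum follow-up.** 20 × 7 = 140, which is less than 168, so 0 days whenever dosing stopped. Only the extension for an unresolved event can change this.

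**Effect on the percentage (illustration).** The documents give neither the share entering the period nor the risk, so both are assumed. With a 20% risk among those who enter and 5% to 30% of the arm entering, the table shows 0.05 × 20% = 1% up to 0.30 × 20% = 6%. With the same 20% risk in both arms but 10% versus 30% entering, it shows 2% versus 6%.

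**Would a denominator of patients with at least one post-treatment day repair this?** Take a hypothetical 60 per arm with 6 who stop early and stay, 3 of whom have an event, and 54 full-course patients. About 54 × 0.467 = 25 full-course patients also qualify through visit timing, so the table shows about 3/31.2 = 9.6%, against 3/6 = 50% among the early stoppers. With 15% versus 5% stopping early (9 and 3 patients) and half of each having an event, the denominators are about 9 + 51 × 0.467 = 32.8 and 3 + 57 × 0.467 = 29.6. The result is 4.5/32.8 = 13.7% versus 1.5/29.6 = 5.1%, still a 2.7-fold gap. These figures assume no events in the full-course patients' few extra days.

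**One discrepancy checked.** The off-drug period heading in Protocol 6.1 ends at Day 700. The 72-week duration, both schedule tables and the SAP windows all point to Day 505, which is used here.

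**The case against.** The strongest case for leaving the tables alone has four parts.

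- Using all treated patients is an ordinary cumulative-incidence convention, and Protocol 11.4.5.1 sets the same denominator for AE incidence. This stands as a defence of the treatment-emergent tables. But that protocol section plans incidence summaries for treatment-emergent events and only a listing for deaths. The post-treatment incidence tables are added by the SAP, and the convention suits them less well.
- The consequence is small. Safety summaries are descriptive with no testing, counts are shown, the SAP puts its main focus on treatment-emergent events, and the 168-day window means that off-drug events are still reported there. This stands and limits the point to minor severity.
- Restricting to patients who reach the period selects them after randomization, and for deaths a common denominator lets the two periods add up. Both stand. They argue for keeping the counts and adding patient-time beside them.
- The trial was discontinued with few patients, so illustrations with 60 per arm do not describe the data to be reported. This also stands.

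A reader might go further and infer that full-course patients have zero post-treatment time by definition, that the percentages are near zero by construction, or that they simply track early stopping. The documents do not support these readings. The period ends at the last visit, not at Day 505, so windows allow up to 11 days. Near-zero values require most patients to be full-course or withdrawn with minimum follow-up, and that mix is not given. Early stopping alone adds no time under minimum follow-up; stopping and remaining in the study does, or an extension for an unresolved event.

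**Conclusion.** The point holds as a minor reporting weakness. The safety-set denominator applies explicitly to post-treatment AEs and SAEs and by implication to post-treatment deaths. It includes patients who contribute 0 nominal days (at most 11) after a full course, or 0 after minimum follow-up. Observed post-treatment time comes mainly from patients who stop drug early and stay, at 28 to 336 days each on the nominal schedule. The percentages therefore cannot distinguish absence of events from absence of observation, and a difference between arms can arise from retention after stopping.

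This rests on Day 505 as the final visit and on the stated windows. The actual distortion cannot be computed, because the documents give neither the last-dose times nor the follow-up after termination. If patients stopped at termination and had only the minimum follow-up, every post-treatment cell would read 0% with no time at risk. That is a conditional statement, not a finding about these data. No formal conclusion of the trial is affected.

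**What to change.** In SAP 5.8.1, for the post-treatment AE, SAE and death tables:

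1. Keep the event and patient counts.
2. Show, by arm, the number of safety-set patients with any follow-up after last dose + 168 days, and the total post-treatment patient-days, computed as the sum of max(0, last visit day − (last dose day + 168)).
3. Report events per patient-time. Do not rely on a denominator of patients with at least one post-treatment day, which still gives equal weight to 1 day and 336 days.
4. Where an arm has no patient-days, print that no post-treatment time was observed, in place of 0%.
5. State beside the tables that the rates rest on little patient-time and on a subset selected after randomization.

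The cost is a short wording change and two derived variables from dates already collected. It needs no new data, leaves the treatment-emergent tables unchanged and requires no change to patient follow-up. The downside is that the rates will be imprecise, which the displayed patient-days make plain.

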#### ***Analysis of all treatment-emergent adverse events***

The following TEAE summaries will be generated:

- Overview of TEAEs, summarizing number (%) of patients with any
  - TEAE;
  - Serious TEAE;
  - TEAE leading to death;
  - TEAE leading to permanent treatment discontinuation.
- All TEAEs by primary SOC, HLGT, HLT, and PT
- All TEAEs by primary SOC and PT
- Number (%) of patients experiencing common TEAE(s) presented by primary SOC and PT (PT incidence  $\geq 5\%$  in any treatment group)
- All TEAEs relationship (related/not related) to evinacumab

- All TEAEs by maximum severity (i.e., mild, moderate or severe)

***Analysis of all treatment emergent serious adverse event(s)***

- All Serious TEAEs by primary SOC, HLT, HLT, and PT
- All Serious TEAEs by primary SOC and PT
- Patient listings of serious TEAEs will be provided in the report appendix.
- All Serious TEAEs relationship (related/not related) to study treatment

***Analysis of all treatment-emergent adverse event(s) leading to treatment discontinuation***

- All TEAEs leading to permanent treatment discontinuation, by primary SOC, HLT, HLT, and PT
- All TEAEs leading to permanent treatment discontinuation, by primary SOC and PT
- Patient listings of TEAEs leading to permanent treatment discontinuation will be provided in the report appendix.

***Post-treatment adverse events***

- All post-treatment AEs by primary SOC and PT
- All post-treatment SAEs by primary SOC and PT

***Analysis of Acute Pancreatitis Events***

- TEAEs suspected of being AP events by primary SOC and PT
- TEAEs suspected of being AP events adjudicated as positive by primary SOC and PT
- TEAEs suspected of being AP events categorized by adjudicated outcome of positive, negative, or in-process (applicable for the interim analyses)
- Patient listing of positively adjudicated TEAE AP events

***Patient Deaths***

The following summaries of deaths will be generated.

- Number (%) of patients who died by study period (TEAE and post-treatment) and reason for death;
- TEAEs leading to death (death as an outcome on the AE CRF page, as reported by the Investigator) by SOC and PT

**5.8.2. Analysis of Adverse Events of Special Interest**

Treatment-emergent adverse events of special interest (AESI), as listed in Section 4.8.1.2, will be presented by SOC and PT as applicable. AESI are defined by dedicated e-CRF.

### **5.8.3. Clinical Laboratory Measurements**

Clinical laboratory parameter actual values (quantitative) and change from baseline values will be descriptively summarized at baseline and each post-baseline visit for the study treatment period, by at least patient number, mean, median, Q1, Q3, SD, minimum and maximum.

Clinical laboratory parameters mean changes from baseline, with the corresponding SE, can be plotted at each visit in the case results warrant further investigation. These parameters will be presented by the biological functions defined in Section 4.8.2. For glucose, only fasting samples will be included in the summaries.

Individual patient laboratory parameter measurements will be additionally evaluated by PCSV criteria (See Appendix 10.3), specifically identifying patients with at least one post-baseline measurement that meets the PCSV criteria within the TEAE period. These laboratory parameters will be presented by the biological functions defined in Section 4.8.2. The incidence of PCSVs at any time during the TEAE period will be summarized regardless of the baseline level, and again according to the following baseline categories:

- Normal (according to PCSV criterion/criteria)/missing
- Abnormal according to PCSV criterion or criteria

Patient listings of laboratory measurements that meet PCSV criteria will be provided for the report appendix.

For those laboratory parameters that don't have an associated PCSV criteria, similar summary tables can be provided based on measurements outside the central laboratory normal ranges, if applicable.

#### ***Drug-induced liver injury***

For the treatment period, an evaluation of drug-induced serious hepatotoxicity (eDISH) with the graph of distribution of peak values of ALT versus peak values of total bilirubin will also be presented using post-baseline values during TEAE period. Note that the ALT and total bilirubin values are presented on a logarithmic scale. The graph will be divided into 4 quadrants with a vertical line corresponding to 3 x ULN for ALT and a horizontal line corresponding to 2 x ULN for total bilirubin.

Patient listing of possible Hy's law cases identified by treatment group (i.e., patients with any elevated ALT > 3 x ULN, and associated with an increase in bilirubin > 2 x ULN, concomitantly or not) with ALT, AST, ALP, total bilirubin, and if available direct and indirect bilirubin will be provided.

The summary of clinical laboratory parameter measurements will be provided by treatment group for the study in the safety analysis set.

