8.3.2.1. Reasons for Permanent Discontinuation of Study Drug

Study drug dosing will be permanently stopped in the event of:

- Evidence of pregnancy
- Severe, acute infusion reactions related to study treatment including, but not limited to, anaphylaxis
- Specific types of liver dysfunction (eg, Hy's law is met ([Guidance for Industry Drug Induced Liver Injury: Premarketing Clinical Evaluation FDA 2009]))

Liver impairment as evidenced by 1 or more of the following criteria and no other reason can be found to explain the following lab abnormalities, such as viral hepatitis A, B, or C; pre-existing or acute liver disease; or another drug capable of causing the observed injury:

- ALT or AST $>8 \times$ ULN, or
- ALT or AST $>5 \times$ ULN for more than 2 weeks, or
- ALT or AST $>3 \times$ ULN and total bilirubin $>2 \times$ ULN (or international normalized ratio [INR] >1.5)
- ALT or AST $>3 \times$ ULN with the appearance of fatigue, nausea, vomiting, right upper quadrant pain or tenderness, fever, rash, and/or eosinophilia ($>5\%$)
- Patient withdraws consent

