### 10.3. Criteria for Potentially Clinically Significant Values (PCSV)

Parameter	PCSV
Clinical chemistry	
ALT	By distribution analysis:  >2 ULN and baseline $\leq$ 2 ULN >3 ULN and baseline $\leq$ 3 ULN >5 ULN and baseline $\leq$ 5 ULN >10 ULN and baseline $\leq$ 10 ULN >20 ULN and baseline $\leq$ 20 ULN
AST	By distribution analysis:  >2 ULN and baseline $\leq$ 2 ULN >3 ULN and baseline $\leq$ 3 ULN >5 ULN and baseline $\leq$ 5 ULN >10 ULN and baseline $\leq$ 10 ULN >20 ULN and baseline $\leq$ 20 ULN
Alkaline Phosphatase	> 1.5 ULN and baseline $\leq$ 1.5 ULN
Total Bilirubin	> 1.5 ULN and baseline $\leq$ 1.5 ULN > 2 ULN and baseline $\leq$ 2 ULN
Conjugated bilirubin	> 35% total bilirubin (when total bilirubin >1.5 ULN)
ALT and Total Bilirubin	ALT > 3 ULN and Total Bilirubin > 2 ULN and baseline ALT $\leq$ 3 ULN or Total bilirubin $\leq$ 2 ULN

Parameter	PCSV
CPK	> 3 ULN and $\leq$ 5 ULN and baseline $\leq$ 3ULN >5 ULN and $\leq$ 10 ULN and baseline $\leq$ 5 ULN >10 ULN and baseline $\leq$ 10 ULN
Creatinine	$\geq$ 150 $\mu$ mol/L (adults) $\geq$ 30% from baseline $\geq$ 100% from baseline
CLcr (mL/min) (Estimated creatinine clearance based on the Cokcroft-Gault equation)	$\geq$ 15 - <30 (severe decrease in GFR) $\geq$ 30 - < 60 (moderate decrease in GFR) $\geq$ 60 - <90 (mild decrease in GFR) $\geq$ 90 (normal GFR)
eGFR (mL/min/1.73m  ) (Estimate of GFR based on an MDRD equation)	$\geq$ 15 - <30 (severe decrease in GFR) $\geq$ 30 - < 60 (moderate decrease in GFR) $\geq$ 60 - <90 (mild decrease in GFR) $\geq$ 90 (normal GFR)
Uric Acid	
Hyperuricemia:	>408 $\mu$ mol/L
Hypouricemia:	<120 $\mu$ mol/L
Blood Urea Nitrogen	$\geq$ 17 mmol/L
Chloride	<80 mmol/L $\geq$ 115 mmol/L
Sodium	$\leq$ 129 mmol/L $\geq$ 160 mmol/L
Potassium	< 3 mmol/L $\geq$ 5.5 mmol/L
Glucose	
Hypoglycaemia	$\leq$ 3.9 mmol/L and < LLN
Hyperglycaemia	$\geq$ 7 mmol/L (fasted); $\geq$ 11.1 mmol/L (unfasted)
HbA1c	>8%
Albumin	$\leq$ 25 g/L
Hs-CRP	> 2 ULN or $\geq$ 10 mg/L, if ULN not provided
Hematology	
WBC	< 3.0 Giga/L (3000/ mm  ) (Non-Black) < 2.0 Giga/L (2000/ mm  ) (Black) $\geq$ 16.0 Giga/L (16000/ mm  )
Lymphocytes	>4.0 Giga/L

Parameter	PCSV
Neutrophils	< 1.5 Giga/L (1500/ mm  ) (Non-Black) < 1.0 Giga/L (1000/ mm  ) (Black)
Monocytes	>0.7 Giga/L
Eosinophils	> 0.5 Giga/L (500/ mm  ) or > ULN if ULN ≥ 0.5 Giga/L

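### SAP 5.8.3 and the combined PCSV row identify possible Hy's law cases on ALT only, while protocol 8.3.2.1 uses ALT or AST, so an AST-only case with raised bilirubin is not flagged

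*SAP*

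**What the plan says.** **SAP 5.8.3, drug-induced liver injury.** The listing of possible Hy's law cases selects "patients with any elevated ALT > 3 x ULN, and associated with an increase in bilirubin > 2 x ULN, concomitantly or not". The listed patients are shown "with ALT, AST, ALP, total bilirubin, and if available direct and indirect bilirubin will be provided", so AST is a printed column but not a way into the listing. The eDISH display is a "graph of distribution of peak values of ALT versus peak values of total bilirubin". On its cut-points: "The graph will be divided into 4 quadrants with a vertical line corresponding to 3 x ULN for ALT", with the horizontal line at 2 x ULN for total bilirubin.

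**SAP 10.3.** The only combined liver criterion begins "ALT > 3 ULN and Total Bilirubin > 2 ULN and baseline ALT". There is no AST counterpart. AST and total bilirubin each have their own single-parameter rows.

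**Protocol 8.3.2.1.** Hy's law is given as an example of liver dysfunction that ends dosing. The liver-impairment criteria that follow apply when "no other reason can be found to explain the following lab abnormalities". One of them is "ALT or AST $>3 \times$ ULN and total bilirubin $>2 \times$ ULN", with INR above 1.5 as an alternative to the bilirubin part.

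**SAP 1.2.4.** The modifications from the protocol's statistical section do not mention the liver criterion.

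**The concern.** The listing exists to pick out patients whose transaminase and bilirubin are both raised. It is built as a broad screen: it accepts elevations that do not coincide and does not ask for other causes to be excluded. Yet on the enzyme it is narrower than the protocol's own stop limb, and no reason is given.

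Elsewhere the documents treat the two enzymes together: the screening exclusion (protocol 7.2.2), the AESI definition (protocol 10.1.3, SAP 4.8.1.2) and the single-parameter PCSV rows. ALT-only selection is the exception.

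At stake is identification. A patient stopped under the AST part of the protocol limb could be absent from the listing meant to show such cases. With few patients and purely descriptive safety reporting, one such patient is the difference between a listing with one entry and an empty one.

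**Working it through.** The plan states no figure to reproduce. The check is logical: apply each rule to every combination of three yes/no findings.

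**Inputs**
- Protocol limb (8.3.2.1): (ALT > 3 x ULN or AST > 3 x ULN) and total bilirubin > 2 x ULN, taking the no-other-cause condition as met and leaving the INR alternative aside.
- SAP listing (5.8.3): ALT > 3 x ULN and bilirubin > 2 x ULN.
- SAP eDISH quadrants (5.8.3): ALT cut at 3 x ULN, total bilirubin cut at 2 x ULN.

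| ALT > 3 | AST > 3 | Bili > 2 | Protocol limb met | In SAP listing | eDISH quadrant |
|---|---|---|---|---|---|
| no | no | no | no | no | normal |
| no | no | yes | no | no | bilirubin only |
| no | yes | no | no | no | normal |
| **no** | **yes** | **yes** | **yes** | **no** | **bilirubin only** |
| yes | no | no | no | no | ALT only |
| yes | no | yes | yes | yes | Hy's law |
| yes | yes | no | no | no | ALT only |
| yes | yes | yes | yes | yes | Hy's law |

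Three of the eight cells meet the protocol limb, and the listing captures two of them. The missed cell is AST raised, ALT not raised, bilirubin raised. The combined PCSV row misses the same cell. With selection on ALT or AST, all three are listed.

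**Worked example.** Take AST 4 x ULN, ALT 2.5 x ULN and bilirubin 2.5 x ULN.
- Protocol limb: 4 > 3 and 2.5 > 2, so it is met if no other cause is found.
- Listing and combined PCSV row: ALT 2.5 is not above 3, so neither is triggered.
- eDISH: the point is drawn, left of the ALT line (2.5 < 3) and above the bilirubin line (2.5 > 2).

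**Where the same patient does appear**
- The AST > 3 ULN PCSV, if baseline AST was at or below 3 ULN, and the bilirubin > 2 ULN PCSV, if baseline bilirubin was at or below 2 ULN. SAP 5.8.3 provides patient listings of PCSVs.
- The ALT/AST AESI. With baseline AST below ULN the threshold is 3 x ULN, and 4 passes. With baseline at or above ULN the threshold is twice baseline, so 4 passes unless baseline exceeded 4 / 2 = 2 x ULN.
- The listing of TEAEs leading to permanent discontinuation (SAP 5.8.1), if the stop is recorded as a TEAE.

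The PCSV rows are separate criteria, the AESI definition contains no bilirubin, and the discontinuation listing is organised by event. None of them marks the enzyme and bilirubin combination.

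**The case against.** The strongest reply is that a dosing-stop rule and a descriptive reporting screen serve different purposes and need not match. Protocol 11.4.5.2 leaves the PCSV criteria to the SAP, and the protocol specifies neither a Hy's law listing nor an eDISH plot. Protocol 8.3.2.1 mentions Hy's law as an example and does not say that its ALT-or-AST limb defines it. All of that stands: this is an unexplained narrowing, not a breach of a protocol-specified analysis. It does not explain why a screen drawn broadly on timing and cause should be narrow on the enzyme.

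Three stronger readings are tempting, and the documents do not support them.
- *The patient is missing from the plot.* No ALT threshold governs entry to the graph; the lines only divide it. The patient is plotted, but in the bilirubin-only quadrant.
- *The case goes unreported.* Protocol 10.1.1 requires isolated laboratory abnormalities that lead to discontinuation to be reported as AEs, protocol 10.1.2 asks for a narrative for AESIs, and the PCSV listings carry the values. With few patients a reader could match these by hand. What is lost is the flag, not the data.
- *The liver conclusion rests on this listing alone.* The SAP also plans PCSV tables and listings, AESI tables and discontinuation outputs.

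It is also fair to say that adding AST does not make the listing cover every stop criterion in protocol 8.3.2.1. The INR alternative and the limbs without bilirubin stay outside it. The case for the change is that the listing is a transaminase-plus-bilirubin screen and should cover that pair as the protocol defines it.

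**Conclusion.** The mismatch is real and the point holds, as a minor one. The SAP's listing and combined PCSV row leave out a patient with AST > 3 x ULN, ALT at or below 3 x ULN and bilirubin > 2 x ULN, and the eDISH graph places that patient outside the Hy's law quadrant. The other outputs show the components without flagging the combination.

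The gap is one of the three patterns that meet the protocol limb, which says nothing about how often it occurs. It arises only when AST and ALT are discordant, and its frequency cannot be derived from the documents. The reading assumes that the protocol's no-other-cause condition is met and sets the INR alternative aside. No estimate, test or error rate is affected, because all analyses in this abbreviated SAP are descriptive. No view is taken on which dosing-stop criterion is right; the protocol and SAP passages need to be reconciled for reporting.

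**What to change.** 1. SAP 5.8.3: select the possible Hy's law listing on *any ALT or AST > 3 x ULN* with bilirubin > 2 x ULN, leaving the rest of the sentence unchanged.
2. SAP 10.3: make the combined row *ALT or AST > 3 ULN and Total Bilirubin > 2 ULN*, with the baseline condition extended to the enzyme that qualifies.
3. eDISH: add a second panel of peak AST against peak total bilirubin with the same cut-points.
4. Note in SAP 5.8.3 that the INR alternative in protocol 8.3.2.1 is not covered, because INR is not among the laboratory tests in protocol 9.2.3.4.

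If ALT-only selection is intended, say so in SAP 1.2.4 and give the reason.

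The cost is a few words, a small program change and one more plot panel. AST and bilirubin are already in the chemistry panel. The downside is an occasional listed case in which AST is not of hepatic origin; CPK from the same panel helps to interpret it.
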